**Consequently, response at the end of six cycles of systemic therapy will be used to guide the use of RT in this trial. Specifically, localized Residual PET Radiation Therapy (Residual PET RT) will be used for patients with limited residual PET-avid sites who have achieved a partial response (as per the 2014 Lugano Classification) at the completion of 6 cycles of systemic therapy on either arm.** This indication for RT to reduce the rate of relapse in this high-risk population is consistent with available evidence and with recent German Hodgkin Study Group trials. (88) This approach is anticipated to reduce the rate of RT in childhood HL patients from 60% to 15% in advanced stage HL.

In advanced-stage or high-risk patients, involved field radiotherapy (IFRT) has traditionally encompassed a large volume of normal tissue due to anatomically widespread sites of multiple disease and extra-lymphatic spread.

One of the aims of this study is to reduce the volume of radiotherapy in order to reduce potential acute and late toxicities, while maintaining disease control.

This will be done in two ways:

- 1) omitting radiotherapy (RT) among patients who have a complete response to systemic therapy (defined as Deauville 1-3 after six cycles of systemic therapy), and
- 2) limiting the volume of RT among patients who receive this treatment by employing Residual PET Radiation Therapy (Residual PET RT).

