### 5.2 Age criteria: Patients must be $\geq$ 12 years of age.

### 5.3 Prior/Concurrent Therapy Criteria

- a. Patients must not have received any prior chemotherapy, radiation, or antibody-based treatment for classical Hodgkin lymphoma. Steroid pre-treatment is permitted as outlined in [Section 5.4k](#)
- b. Patients must not have had prior solid organ transplant.
- c. Patients must not have had prior allogeneic stem cell transplantation.
- d. Patients must not have received a live vaccine within 30 days prior to planned Day 1 of protocol therapy (e.g. measles, mumps, rubella, varicella, yellow fever, rabies, BCG, oral polio vaccine, and oral typhoid).

e. At registration, investigator must declare intent-to-treat with Residual PET Radiation Therapy (Residual PET RT- RPRT) to be administered after patient completes 6 cycles of therapy if, after end of treatment, the patient meets criteria specified in [Section 7.5](#) for receiving RT). Patients will be stratified by investigator's intent-to-treat with Residual PET RT.

- All pediatric patients (< 18 years of age) will be considered intent-to-treat with Residual PET RT at time of registration.

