- o. Females of childbearing potential must not be pregnant or nursing, and have a negative pregnancy test within 28 days prior to registration. Women/men of reproductive potential must have agreed to use an effective contraceptive method while receiving study drug and for women until 6 months after receiving the last dose of study drug or, for men, until 7 months after receiving the last dose of study drug. A woman is considered to be of "reproductive potential" if she has had menses at any time in the preceding 12 consecutive months. In addition to routine contraceptive methods, "effective contraception" also includes heterosexual celibacy and surgery intended to prevent pregnancy (or with a side-effect of pregnancy prevention) defined as a hysterectomy, bilateral oophorectomy or bilateral tubal ligation. However, if at any point a previously celibate patient chooses to become heterosexually active during the time period for use of contraceptive measures outlined in the protocol, he/she is responsible for beginning contraceptive measures.

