##### a. Eligibility for protocol-specified radiation therapy Residual PET RT

1. The treating investigator must have declared intent for use of Residual PET RT at the date of registration to the protocol (and patient must meet criteria for RT indications in [Section 7.5b](#)).
2. Timing of protocol therapy administration, response assessment studies, and surgical interventions are based on schedules derived from the experimental design or on established standards of care.

Minor unavoidable departures (up to 72 hours) from protocol directed therapy and/or disease evaluations (and up to 1 week for surgery) for valid clinical, patient and family logistical, or facility, procedure and/or anesthesia scheduling issues are acceptable (except where explicitly prohibited within the protocol).

See also [Section 7.1b](#) for extended allowable windows in event of COVID-19 extenuating circumstance.

3. All investigators registering pediatric patients are required to agree to intent to apply RT per the disease and response characteristics defined below. Investigators at all other (non-COG) participating institutions will be required to have declared their intent to apply RT prior to patient registration and randomization (per [Section 5.3e](#)).
4. IROC Rhode Island will verify patient eligibility for protocol-specified RT. To allow for IROC Rhode Island review prior to RT, images must be submitted to IROC Ohio (via TRIAD preferred) as indicated in [Sections 12.3](#) and [15.4](#).

b. Indications for Radiotherapy

1. The indication for RT will be based on the end-of-treatment imaging evaluation performed upon completion of 6 cycles of systemic therapy (4-8 weeks after the last dose of study drug). In general terms, RT will be delivered when patients have 1-2 sites initially involved with HL that achieve only a partial response. Specifically, RT will be indicated when the patient has persistent sites upon completion of 6 cycles of systemic therapy that meet all of the following criteria:
  - a. Residual nodal mass  $\geq 2.5\text{cm}$  in axial diameter, or residual extranodal lesion  $>1\text{cm}$  in axial diameter (e.g. lung nodule or splenic nodule), and
  - b. Deauville score = 4 or 5 (See [Section 10.1a](#)), and
  - c.  $\geq 30\%$  reduction in maximal transverse diameter compared to pre-treatment imaging.
2. RT may be given to one or two nodal sites. RT to more than two nodal sites is not allowed.

c. Contraindications for RT:

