RT monitoring: The use of RT will almost exclusively be on the pediatric population, but due to the concern appropriate use in N-AVD arm given the potential of false progressions, it will be monitored closely throughout the study. The DSMB will be provided rates of radiotherapy used in each arm (and within the 12-17 years and  $\geq$  18 years age groups in each arm) for each meeting. The committee will monitor the rate of radiotherapy in both arms and by age group to ensure that there is no overuse in the experimental arm (Arm 1). Due to variability in early event calculations focus on this analysis will not commence until after 30 patients have completed RT. At that point, if there is greater than 15% difference between arms, then the additional communication to NCI and study team for protocol amendment would be considered. This substantive threshold for action in rates is motivated by limited sample sizes and by a slightly higher expected baseline rate of RT use in the N-AVD arm based on the ECHELON-1 and CheckMate 205 studies. If after 75 patients have received RT, then a smaller difference (10%) would be considered a concern and warrant additional discussion with NCI and the study team. We will apply the same rules to RT differences within each age group in each arm.

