Intravenous contrast is recommended for RT planning CT scans. In cases where the lymph nodes are difficult to visualize following chemotherapy, the CTV should encompass a symmetric expansion around the major pelvic vessels of at least 10 mm.

For female patients, MRI simulation and/or fusion of pelvic MRI with planning CT should be performed to contour the ovaries and facilitate estimation of ovarian dosimetry. Females should have consideration for an oophorectomy moving the ovaries away from the PTV volume. The male gonads should also be shielded using a clam-shell type block, as appropriate. Positioning the legs apart may facilitate testicular shielding.

g. Pericardium

Whole pericardial irradiation is contra-indicated. If the pericardium was extensively involved by lymphoma and is part of the CTV definition, the mean dose to the heart should be limited to < 15 Gy. In circumstances where this cannot be achieved, the treating oncologist should review the case with a study investigator.

h. Sites of metastatic disease or isolated extranodal disease (lung, liver, bone)

Sites of metastatic or isolated extranodal disease are treated only if they meet the criteria listed above. Whole organ irradiation is contraindicated. For PET avid lung nodules, the involved portion of lung (or lungs) should be treated with at least a 1.5 cm margin. Patients presenting with a pleural effusion should not receive treatment to the whole hemithorax. Similarly, isolated liver or bone lesions meeting criteria for RT may be treated with GTV, CTV, and PTV definitions as described above. Whole liver or bone RT is not required.

i. Solitary Bone or Bone Marrow Lesion

A skeletal lesion seen on FDG-PET should only be considered true bone lesion if there is an associated bone abnormality seen on CT at the time of diagnosis. Abnormal sites involving the skeleton without an associated CT abnormality should be considered as bone marrow involvement.

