**4. Case Selection (if applicable)**

As a first step, we will analyze the first half of patients enrolled to the study, who will have sufficient follow-up and a full set of specimens - baseline, C3D1, EOT, relapse (if applicable). We anticipate that about 80% of patients will have the full set of serial specimens. As of May 15, 2022, there were currently 400 patients with paired baseline, C3D1, EOT, and paired normal buffy coat samples banked at the SWOG biorepository. We will also analyze patients who progress on therapy but have baseline and at least one on-treatment sample (and paired baseline buffy coat specimen). We will reserve the samples from patients enrolled to the second half of the study for validation purposes and/or to further interrogate preliminary findings from the initial analysis.

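### The pelvic radiotherapy guidance names an operation that removes the ovaries where its stated aim is to move them

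*Combined protocol and SAP*

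**What the plan says.** Section 18.6f, item 7f, tells sites how to plan Residual PET RT to pelvic lymph nodes. For females, pelvic MRI, by simulation or by fusion with the planning scan, "should be performed to contour the ovaries and facilitate estimation of ovarian dosimetry". The next sentence reads: "Females should have consideration for an oophorectomy moving the ovaries away from the PTV volume". The one after that says the male gonads should also be shielded.

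The word appears in one other place. Section 5.4o lists surgery that counts as contraception, "defined as a hysterectomy, bilateral oophorectomy or bilateral tubal ligation".

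The guidance reaches two groups of females:

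- **Patients under 18.** Section 5.3e counts all of them as intended for Residual PET RT. Section 11.2 adds: "The use of RT will almost exclusively be on the pediatric population".
- **Adults whose investigator declared the intent.** Section 5.3e: "At registration, investigator must declare intent-to-treat with Residual PET Radiation Therapy". Section 7.5a.3: "Investigators at all other (non-COG) participating institutions will be required to have declared their intent to apply RT" before registration and randomization.

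**The concern.** The named operation and its purpose conflict within one sentence. Removing an ovary does not move it out of the planning target volume, and it defeats the protection that the surrounding text is meant to give.

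Section 18.6 is guidance that sites act on, not background. Eligibility starts at age 12, and Section 2.5 itself counts infertility as a heavy burden in a disease of the young. A site that followed the sentence literally would be considering an irreversible operation with the opposite effect to the one intended. No endpoint, error rate, sample size or analysis is touched.

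**Working it through.** **1. Which sense the context requires.** The documents give no figure on this point, so the texts are set side by side.

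| Place | What it implies |
|---|---|
| 18.6f.7f, preceding sentence | The ovaries are contoured and their dose estimated, so they stay in the body |
| 18.6f.7f, the sentence itself | The aim is to move the ovaries away from the target |
| 18.6f.7f, following sentence | Male gonads are *also* shielded, so the subject is gonadal protection |
| 5.4o | The same word, listed with hysterectomy and tubal ligation, means removal |

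Three of the four concern gonads that stay in the body. The fourth shows that the protocol uses the word in its ordinary sense. No section redefines or corrects it. The contradiction is real on the supplied text. That transposition was meant is an inference, since no section names that operation.

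**2. How many patients the sentence could concern.** The planned enrolment tables in Section 2.9 give these numbers of females:

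- Pediatric: domestic 128 + 28 = 156; international 16 + 0 = 16; total 172.
- Adult: domestic 230 + 23 = 253; international 25 + 2 = 27; total 280.
- All females: 172 + 280 = 452.
- All patients: 579 + 64 + 317 + 27 = 987, so 452/987 = 45.8% are female.

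The step from 452 to females given pelvic RT cannot be made. The documents give no pelvic share, no share of adults with declared RT intent and no expected adult RT rate. Section 2.6 gives an expectation for childhood patients only: "This approach is anticipated to reduce the rate of RT in childhood HL patients from 60% to 15% in advanced stage HL".

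**3. How many a correction could still reach.** Section 18.13c.4 reports: "As of May 15, 2022, there were currently 400 patients with paired baseline, C3D1, EOT, and paired normal buffy coat samples banked". Section 7.5e starts RT 5 to 12 weeks after Cycle 6 Day 15. Twelve weeks after May 15, 2022 is August 2022, about a year before the 9/2/2023 version.

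- Past the RT start window by then: at least 400/987 = 40.5%.
- Remaining: at most 987 − 400 = 587.
- Female at the planned mix: 587 × 0.458 ≈ 269.

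This is a loose ceiling because it ignores the patients treated between May 2022 and September 2023. A closer estimate needs assumptions:

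- Accrual starts at the July 19, 2019 posting shown in Section 18.12 and runs uniformly over 4 years (Section 11.1), ending July 19, 2023.
- Cycle 6 Day 15 falls 22 weeks after Cycle 1 Day 1 (5 × 28 + 14 = 154 days). Up to 2 weeks from registration to treatment and 12 weeks to RT make 34 to 36 weeks in all.
- Patients registered in the last 193 days of accrual (34 weeks) or 207 days (36 weeks) are then not yet past the window.
- 987 × 193/1461 ≈ 130 and 987 × 207/1461 ≈ 140 patients; times 0.458, about 60 to 64 females.

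Both figures are pools before the three RT criteria, the limit of one or two sites and the unknown pelvic share are applied. Neither counts patients at risk.

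**The case against.** **It may be a reading error.** The text was extracted by machine, and the correct word shares its stem with the printed one. The extraction does slip: the same imaging-form link ends in four different codes across Sections 14.4a, 14.4f (twice) and 14.4i. This cannot be excluded, and the finding is conditional on it. But those slips are in arbitrary character strings, whereas here one valid medical term would have replaced another, which seems less likely.

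**No specialist would misread it.** The sentence states its aim and asks only for consideration. RT is at the physician's discretion (Section 7.5), and study radiation oncologists can be consulted (Section 18.6f.5). RT data must also go for central review and approval a week before treatment (Sections 12.3 and 18.6l). This stands, and it is why the point is minor. The central review does not expressly cover surgery, though, and low risk does not make the sentence right.

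**The headcounts do not measure the problem.** That is fair: none is a count of pelvic RT. The 400 is also not a strict bound, because Section 7.5e allows RT to wait until blood counts recover. The figures show only that the remaining reach is limited.

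**Conclusion.** The point holds, as a minor correction. On the supplied text, Section 18.6f.7f names an operation that contradicts its own stated aim. The context makes this a wording error and not a design choice.

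Its size in patients cannot be derived. The outer pool is 452 planned females. At most about 269 were still ahead of the RT window at the 9/2/2023 version, or about 60 to 64 under uniform accrual from July 2019, and only an unknown fraction of them would receive pelvic RT. These figures assume the planned sex mix and RT starting inside the 12-week limit.

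Confidence is medium, because the finding rests on one word in machine-read text. If the source PDF already names a transposition procedure, the finding falls away.

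**What to change.** 1. Check the word in the source PDF.
2. If it is there, have the radiation-oncology lead confirm the intended procedure, then replace *oophorectomy* in Section 18.6f.7f with *oophoropexy (ovarian transposition)*. Section 5.4o is correct and stays as it is.
3. Put the change in the next revision, through the usual CIRB or local IRB approval and site activation, with a short notice to sites.

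The cost is one word, one specialist confirmation and a site notice. No procedure, data item or analysis changes.

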1. Deauville score 5 due to development of new PET avid sites during systemic therapy.
2. Three or more persistent PET-avid (Deauville score 4-5) sites at completion of systemic therapy.
3. An end-of-treatment PET-avid lesion contained within a mass that is measurable by CT scan and has not achieved at least 30% reduction in transverse diameter since initiation of therapy.

Patients with the above features are unlikely to be cured with RT, and *biopsy with alternative management should be considered*.

d. Radiotherapy Dose and Schedule for SRL Lesions

Radiotherapy will consist of 3000-3600 cGy in fractions of 150-200 cGy per day.

1. The treatment will be given 5 days per week.
2. All fields should be treated once each day.
3. The total elapsed treatment time will be approximately 4 weeks.

e. Timing of Radiotherapy and Starting Criteria

Treatment should begin 5-12 weeks from Cycle 6, Day 15 of chemotherapy or when blood counts have recovered.

Criteria include an ANC > 750/ $\mu$ L and platelets > 75,000/ $\mu$ L prior to treatment for each site.

f. Credentialing Requirements

See [Section 18.6d](#) for credentialing requirements.

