It is not necessary to treat initially involved sites that have achieved an anatomic and metabolic Complete Response. The indications for RT are outlined in [Section 18.6a](#) and should be the principal determinants in defining the gross tumor volume (GTV), the clinical target volume (CTV) and the planning target volume (PTV).

Note: The following definitions apply only to sites of disease that meet the criteria for receiving RT.

1. Post-Chemotherapy GTVtotal

Following completion of 6 cycles of systemic therapy, the post-chemotherapy GTVtotal includes persisting imaging abnormalities seen on CT that encompass a PET-avid site (Deauville 4-5). Note that for RT planning purposes, this includes the parts of that mass that are PET-negative. The GTV (and CTV) are not just the PET-avid volume within the persistent CT abnormality. Residual nodal masses must be  $\geq 2.5$  cm in greatest axial diameter and residual extranodal lesions (lung nodules, splenic nodules) must be  $\geq 1$  cm to be eligible for RT. The CTV and PTV encompassing the GTVtotal are to be prescribed 30Gy.

GTVPET+: This is defined as the volume of imaging abnormality that remains PET avid (Deauville score 4-5) following completion of 6 cycles of systemic therapy. This volume is contained within, and is typically smaller than, the post-chemotherapy GTVtotal defined above. This volume, and its surrounding PTV, should be boosted with an additional 6Gy (total 36Gy) provided the boost does not cause the normal tissue dose limits described below to be exceeded. The boost is not required if it causes the normal tissue constraints to be exceeded. When a boost is to be employed, a CTV expansion is not required around the GTVPET+ volume, although an ITV/PTV expansion is required.

2. Post-Chemotherapy Clinical Target Volume (CTV)

For this study, the CTV should encompass the GTVtotal volume described above, plus any additional volume that may be required to account for uncertainty in disease localization due to variation in imaging, patient positioning, etc. Since the at-risk CT abnormality encompasses the PET-avid volume, this volume will almost always be larger than the GTVPET+ volume.

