RT is only indicated for true bone involvement that remains PET avid (Deauville 4-5) at completion of systemic therapy. Bone sites meeting the criteria for RT should be treated with at least a 1 cm margin around the radiological abnormality. No more than 2 sites should be considered for radiation. Some residual metabolic activity in bone may reflect bony healing, and thus interpretation within the context of the response of other involved areas may be appropriate. In these situations, WebEx conference between IROC, treating institutions and study committee chairs should be considered. The sites can be determined in evaluation and review with IROC.

g. Target Dose

The dose to the GTVtotal, CTVtotal, and PTVtotal, should be 3000-3600 cGy in 150-200 cGy fractions, with a sequential or concurrent boost of 600 cGy to the PET avid volume (GTVPET+/PTVPET+).

1. Dose Definitions

The absorbed dose is defined in centigray (cGy)-to-muscle. Proton dose will be reported in Gy (relative biological effectiveness, RBE), where 1 Gy (RBE) = proton dose Gy x RBE, and RBE = 1.1.

2. Plan Normalization

There are several ways in which plans can be normalized, most commonly normalization to a point or to an isodose surface. In all cases the isodose coverage around GTV, CTV and PTV should be evaluated and the dose uniformity requirements indicated below should be satisfied. If normalization is to a point, the point should be in solid tissue, not in lung. If the central axis falls beneath a block in any field, an appropriate off-axis point may be used for calculations.

3. Heterogeneity corrections

Calculations must take into account tissue heterogeneity and should be performed with CT-based treatment planning to generate dose distributions and treatment calculations from CT densities. When treatment beams traverse lung, planning must be performed using an approved dose calculation algorithm. Approved algorithms include: convolution superposition, collapsed cone convolution, and Monte Carlo. When protons are used, correlation between the institutional CT treatment planning system Hounsfield Units and "relative proton stopping power" must be established and documented. Proton therapy should be used with extreme caution when any of the treatment beams traverse normal lung parenchyma.

4. Dose Uniformity

For all treatments, 95% of the prescription dose must cover  $\geq 99\%$  of the CTV and  $\geq 95\%$  of the PTV.

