For patients not receiving a 6Gy boost, no more than 10% of the CTV or PTV should receive more than 110% of the protocol dose (i.e. 3300cGy).

Concurrent boost will produce allowable dose inhomogeneity within the GTVtotal, CTVtotal and PTVtotal. For patients receiving a 600cGy boost, 95% of the total 3600cGy dose (i.e. 3420cGy) must cover  $>95\%$  of the PTVPET+ volume, and no more than 10% of the PTVPET+ volume should receive more than 110% of the protocol dose (i.e. 3960cGy).

In addition, 95% of the prescription dose should cover  $\geq 95\%$  of the PTV and  $\geq 99\%$  of the CTV. The maximum dose in the patient should not exceed 110% of the prescription dose.

No more than 0.03 cc of the PTV should receive less than 85% of the prescription dose.

- If  $> 0.03$  cc of the PTV receives 75-85% of the prescription dose, this will be a minor deviation.
- If  $> 0.03$  cc of the PTV receives  $<75\%$  of the prescription dose, this will be a major deviation.

a. Proton Specific Guidelines:

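### Section 18.6g gives 3000-3600 cGy to the whole radiotherapy target and then adds a 600 cGy boost, which literally allows 4200 cGy where the protocol elsewhere states a total of 3600 cGy

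*Combined protocol and SAP*

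**What the plan says.** Section 18.6g sets the dose for the total volumes (GTVtotal, CTVtotal and PTVtotal): it "should be 3000-3600 cGy in 150-200 cGy fractions, with a sequential or concurrent boost of 600 cGy to the PET avid volume". The boosted volume is named there as GTVPET+/PTVPET+, and 18.6f.1 defines it as lying inside GTVtotal.

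The same appendix gives the dose in three other places, and the treatment section repeats one of them:

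- **18.6f.1, whole target:** "The CTV and PTV encompassing the GTVtotal are to be prescribed 30Gy".
- **18.6f.1, PET-avid part:** "This volume, and its surrounding PTV, should be boosted with an additional 6Gy (total 36Gy", unless the boost would break the normal-tissue limits.
- **18.6g.4, boosted patients:** "95% of the total 3600cGy dose (i.e. 3420cGy) must cover" more than 95% of PTVPET+, and "no more than 10% of the PTVPET+ volume should receive more than 110% of the protocol dose (i.e. 3960cGy".
- **18.6g.4, unboosted patients:** a limit introduced by "For patients not receiving a 6Gy boost" allows at most 10% of the CTV or PTV above "110% of the protocol dose (i.e. 3300cGy".
- **18.6b and 7.5d, the course as a whole:** "Radiotherapy will consist of 3000-3600 cGy in fractions of 150-200 cGy per day". Neither adds a separate boost.

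**The concern.** The 3000-3600 cGy range fits a whole course: 3000 cGy without the boost, 3600 cGy with it. In 18.6g the range is attached to the total volumes, and the boost is then added for a volume nested inside them. The sentence therefore puts the course range where the 3000 cGy base dose belongs, and the two doses add up to more than any other section allows.

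What is at stake is the clarity of an operative dose instruction. Section 11.2 expects radiotherapy to be used almost entirely in the pediatric population, and sections 2.6 and 7.5 state an aim of limiting acute and late toxicity. A secondary issue is plan grading: 18.6m judges deviations against the protocol dose, and 18.6g leaves that dose open to two readings.

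**Working it through.** **Inputs**

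- 18.6g: base dose 3000-3600 cGy to the total volumes; boost 600 cGy.
- 18.6f.1: base 30 Gy (3000 cGy); boost 6 Gy (600 cGy); total 36 Gy (3600 cGy).
- 18.6g.4: 3300 cGy limit (no boost); 3600 cGy total, 3420 cGy coverage level and 3960 cGy limit (with boost).
- 18.6m: more than 115% of protocol dose to 10% of the PTV is an unacceptable deviation.

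**Step 1. Reproduce the plan's own figures from a 3000 cGy base**

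- Boosted total: 3000 + 600 = 3600 cGy.
- Boosted coverage level: 0.95 × 3600 = 3420 cGy.
- Boosted upper limit: 1.10 × 3600 = 3960 cGy.
- Unboosted upper limit: 1.10 × 3000 = 3300 cGy.

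All four match 18.6g.4 exactly, and with a 600 cGy boost they do so only if the base is 3000 cGy.

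**Step 2. Apply 18.6g literally**

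- PET-avid volume, lower end: 3000 + 600 = 3600 cGy.
- PET-avid volume, upper end: 3600 + 600 = 4200 cGy.

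**Step 3. Compare the upper end with the other sections**

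- Against the stated total: 4200 − 3600 = 600 cGy over (4200/3600 = 116.7%). The excess over the top of the course range in 7.5d and 18.6b is the same.
- Against the boosted limit: 4200 − 3960 = 240 cGy over.
- Against 18.6m, taking 3600 cGy as the protocol dose: 1.15 × 3600 = 4140 cGy, so 4200 cGy falls in the unacceptable class.
- Break-even base dose: 3960 − 600 = 3360 cGy. Any base above this takes the boosted total past 3960 cGy.

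The 3960 cGy figure is a volume constraint, not a ceiling on the prescription. A 4200 cGy prescription would nevertheless place nearly all of PTVPET+ above it. The further rule in 18.6g.4 that the maximum dose stay within 110% of the prescription would not reveal the problem if 4200 cGy were itself taken as the prescription, because 1.10 × 4200 = 4620 cGy.

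**Step 4. Unboosted plan at the top of the 18.6g range**

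- 3600/3000 = 120% of the base dose.
- 3600 − 3300 = 300 cGy over the unboosted limit.

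**The case against.** The strongest reply is that the range already includes the boost. GTVPET+ lies within GTVtotal, and 18.6g.4 accepts that a concurrent boost makes the dose uneven across the total volumes. On that view 3000-3600 cGy describes 3000 cGy outside the PET-avid part and 3600 cGy inside it, and neither excess arises. This is a plausible account of what was intended and agrees with 18.6f.1. The sentence does not say it, however: it assigns the range to the total volumes and the 600 cGy to another named volume.

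The second reply is that other text prevents harm. Sections 18.6f.1 and 18.6g.4 both give 3600 cGy as the boosted total, and 12.3 and 18.6 require treatment plans to be submitted a week ahead for central review and approval. Section 7.1b also bars radiotherapy from starting before approval, though the item sent for review there is the end-of-treatment PET-CT. All of this stands and is why the practical risk is low. It guards against a wrong instruction but does not make the instruction right.

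The third reply is that exposure can be bounded. Section 2.6 anticipates a 15% radiotherapy rate in childhood patients, and section 2.9 plans 317 + 27 = 344 pediatric patients, so about 0.15 × 344 = 52 would receive radiotherapy. That is the number treated under these guidelines, not the number misdosed, for which the documents give no basis.

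**Conclusion.** The concern holds as a minor internal inconsistency. Taken literally, 18.6g permits 4200 cGy to the PET-avid volume, against a stated total of 3600 cGy (600 cGy over) and a volume-based limit of 3960 cGy (240 cGy over). It also permits an unboosted 3600 cGy plan, 300 cGy above the limit for such patients.

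The sizes rest on the literal reading at the top of the range; a planner who follows 18.6f.1 arrives at 3600 cGy. Delivery of 4200 cGy is unlikely given central plan review. Endpoints, sample size, power and alpha are not affected.

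**What to change.** Replace the 18.6g sentence so that it does three things:

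- prescribes 3000 cGy, in fractions of 150-200 cGy, to GTVtotal, CTVtotal and PTVtotal;
- adds 600 cGy to GTVPET+/PTVPET+, concurrently or sequentially, where the normal-tissue limits referred to in 18.6f.1 permit;
- states the resulting total to the PET-avid volume as 3600 cGy.

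The course range in 7.5d and 18.6b can stay, since it fits 3000 cGy unboosted and 3600 cGy boosted. The spleen rule in 18.6f.7, which makes the boost optional, is also compatible. The radiation oncology chairs should confirm the wording.

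The cost is a one-sentence correction, with no change to data collection, endpoints or analysis.
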